2.2 Study Procedure and Assessment

The trial will consist of a Pre-Screening Period (within 6 months from time enrollment, to confirm molecular eligibility), Screening Period (28 days, to determine eligibility), a 2-day PK run-in, Treatment Period (21-Day cycles), an End of Treatment (EOT) Visit (occurring after the last dose and within 7 days after the discontinuation of trial treatment date), a Safety Follow-up Visit (occurring within 30 days \pm 14 days after the last dose of trial treatment), and a Long-Term Follow Up period (for up to 24 months after the discontinuation of treatment date). The end of Trial is defined as the date of the last visit (including all follow-up visit) of the last participant in the trial.

2.3 Sample Size

The approximate total number of participants for this trial is 52 evaluable patients. This will include approximately 36 participants in dose escalation (both monotherapy and combination therapy) and 16 participants in backfill cohorts. Additional participants may be added to account for non-DLT evaluable participants in the dose escalation cohorts and participants in backfill cohorts with less than 1 full cycle of treatment.

[figure not shown]
The sample size for dose escalation is not driven by statistics but determined based on number of dose escalations that will potentially be assessed. It is estimated that approximately 12 participants (up to 4 dose levels) are needed for the monotherapy dose escalation (Arm 1) due to the minimum toxicity expected, and approximately 24 participants for the combination escalation phase (Arm 2) with estimated up to 5 potential dose levels for the combination.

3. STUDY OBJECTIVES AND ENDPOINTS

3.1 Objectives

3.1.1 Primary Objectives

[figure not shown]
- To assess the safety and tolerability of RP-3467 alone and in combination in participants with eligible, advanced solid tumors and to define the MTD or MAD for RP-3467 monotherapy

[figure not shown]

3.2 Endpoints

3.2.1 Primary Endpoints

- DLTs, incidence and severity of TEAEs

4. ANALYSIS POPULATIONS

[figure not shown]
The following analysis populations will be used for statistical analysis.

4.1 DLT Evaluable Population

The DLT Evaluable Population will consist of participants who have met the minimum safety evaluation requirements of the trial and /or who experience a DLT at any time during the DLT evaluation period (from the start of treatment through the end of Cycle 1). Minimum safety requirements will be met if, during Cycle 1 of treatment, the participant receives at least 75% of their planned total dose of RP-3467 and olaparib (if applicable), completes required safety evaluations and is observed through the end of Cycle 1 since the first dose of trial intervention. Administration of growth factors or transfusions during the DLT evaluation period for hematologic events not meeting DLT criteria will render a participant not DLT evaluable. DLT evaluability will be recorded in the appropriate CRF and used to determine the DLT evaluable population. The DLT evaluable population will be used to determine DLT rate of the dose levels.

4.2 Safety Population

The Safety Population, used for the assessment of overall safety and tolerability, will consist of all participants who receive at least 1 dose of RP-3467. The analysis set will be used for individual listings, disposition summary table and all safety analyses, unless otherwise specified.

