5.1 Definition of Baseline

For all evaluations unless otherwise noted, baseline is defined as the most recent non-missing measurement prior to the first administration of RP-3467 or olaparib, whichever occurs first.

- Change from baseline is calculated as (Value at a visit – Baseline Value)
- Percent change from baseline is calculated as (Value at a visit – Baseline value)/Baseline value * 100

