10.1 Dose Limiting Toxicities (DLT)

The number of DLTs will be summarized by treatment arms for the DLT Evaluable Population. A toxicity will be considered a DLT if it occurs from the first dose to the end of Cycle 1 [REDACTED]
[REDACTED], meets the pre-defined criteria for DLTs, is deemed at least possibly related to trial treatment, and is not clearly and incontrovertibly due to disease progression or extraneous cause. Toxicity will be assessed using CTCAE v5.0, unless other specified. Details of DLTs will be listed.

DLTs will be defined as any of the following:

- Any death not clearly due to the underlying disease or extraneous causes

Hematologic TEAEs:

- Grade 4 neutropenia
- Febrile neutropenia (defined as absolute neutrophil count (ANC) <1000 cells/ μ L with a single temperature of 38.3°C [100.4°F] for > 1 hour).
- Grade 4 thrombocytopenia or Grade 3 thrombocytopenia associated with Grade \geq 2 bleeding.
- Grade 4 anemia or Grade 3 anemia requiring red blood cell (RBC) transfusion given to participants with documented anemia-related symptoms.

Non-Hematologic TEAEs:

- Any Grade \geq 3 TEAE except the below
 1. Grade \geq 3 non-hematologic laboratory abnormalities that are asymptomatic and respond to medical intervention or resolve to grade 1 in \leq 72 hours.
 2. Grade 3 fatigue with duration < 7 days
 3. Grade \geq 3 nausea/vomiting/diarrhea that lasts \leq 72 hours and resolves with or without optimal supportive care.
 4. Grade \geq 3 amylase or lipase elevation not associated with symptoms or clinical manifestations of pancreatitis.
 5. The use of red blood cell transfusion for anemia Grade <3 or the use of G-CSF for Grade <4 neutropenia
- Symptomatic Grade \geq 3 QTc prolongation (QTcF \geq 501 msec on at least two separate ECGs), or asymptomatic Grade \geq 3 QTc prolongation that has been confirmed by repeat testing and reevaluation by a qualified person and persists after correction of reversible causes such as electrolyte abnormalities or hypoxia.
- Drug-induced liver injury meeting Hy's Law criteria defined as:
 1. ALT or AST \geq 3-fold above the Upper Limit of Normal (ULN) or \geq 5.0 x ULN in the case of liver metastases at baseline and
 2. Serum total bilirubin \geq 2-fold above ULN (without findings of cholestasis) and

3. Alkaline phosphatase < 2 x ULN and
4. No other overt reason for liver injury

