10.2 Adverse Events

All reported AEs will be coded using the Medical Dictionary for Regulatory Activities (MedDRA) with the most current version for the purposes of summarization. NCI CTCAE Version 5.0 will be used for grading AEs. AEs will be collected and recorded for each patient from the day of signing the ICF until 30 days after last trial intervention administration or until participant started alternative anticancer therapy, whichever is sooner. Prior to receiving trial intervention, only AEs considered related to trial procedures and all SAEs will be summarized by arm, dose level, and dose schedule.

A treatment-emergent adverse event (TEAE) will be defined as any event that was not present prior to the initiation of trial intervention(s) or any event that worsens in either intensity or frequency following exposure to trial intervention(s) through 30 days after cessation of trial treatment, or until the participant starts alternate anti-cancer therapy, or the participant is taking the monotherapy treatment and starts the co-therapy olaparib, whichever occurs first. The exception are RP-3467 related SAEs which were reported until the end of trial and will be included as TEAE regardless of time of onset.

All AEs reports will be summarized by treatment regimen (Arm 1 and Arm 2), dose level and schedule (if applicable) unless otherwise specified.

Overall AE summaries will be presented for the Safety Population (unless otherwise specified). The summaries will include the following categories:

- All TEAEs
- TEAEs with CTCAE Grade 3
- TEAEs with CTCAE Grade 4
- TEAEs with CTCAE Grade 5
- DLT (based on DLT evaluable population)
- RP-3467 related TEAE
 - RP-3467 related TEAE with CTCAE Grade 3
 - RP-3467 related TEAE with CTCAE Grade 4
 - RP-3467 related TEAE with CTCAE Grade 5
- Olaparib related TEAE
 - Olaparib related TEAE with CTCAE Grade 3
 - Olaparib related TEAE with CTCAE Grade 4
 - Olaparib related TEAE with CTCAE Grade 5
- Any Serious AEs
- Any treatment-emergent serious AEs (TESAE)
- RP-3467 related TESAEs
- TEAE leading to dose reduction
- TEAE leading to dose interruption
- TEAE leading to study drug withdrawal
- RP-3467 related TEAE leading to dose reduction
- RP-3467 related TEAE leading to dose interruption

- RP-3467 related TEAEs leading to study drug withdrawal
- Olaparib related TEAE leading to dose reduction
- Olaparib related TEAE leading to dose interruption
- Olaparib related TEAE leading to study drug withdrawal

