- r. **Paired Biopsies (Arm 1 Only):** Tumor biopsies will be collected during Screening and on C1D17 (+2 days) 1-4 hours post-dose. Participants must have had a minimum of 3 consecutive days of dosing with trial intervention prior to the on-treatment biopsy collection. If biopsy collection at this timepoint is not possible, the Sponsor should be contacted to get approval for collection on an alternative day. Once approved, the participant should have the biopsy as soon as possible after the participant has received at least 3 consecutive days of trial intervention.
- s. **Optional Post-Progression Tumor Biopsy:** An optional tumor biopsy will be requested post-progression for participants with prior confirmed responses or prolonged stable disease to evaluate mechanisms of resistance.
- w. **Tumor Assessment:** Tumor assessments by disease-appropriate standard criteria (RECIST v1.1) using CT/MRI with contrast of known sites of disease as clinically indicated. A baseline tumor assessment must be performed within 28 days of the first dose. Subsequent assessments must be performed every 6 weeks (\pm 7 days) from C1D1 for the first 3 assessments (~5 months/22 weeks on-treatment), or sooner if clinically indicated. Thereafter, assessments must be performed every 9 weeks (\pm 7 days). Per RECIST v1.1, complete response or partial response should be confirmed; tumor imaging for confirmation of response must be performed at least 4 weeks after the first indication of response. The subsequent tumor imaging after the confirmation of response should be obtained per the original scheduled interval from the confirmatory scan (6 weeks \pm 7 days during the first ~5 months of trial treatment or every 9 weeks thereafter). For participants with prostate cancer, radionuclide bone scans will be required at baseline and on the same schedule as the RECIST assessments for the assessment of bone disease per PCWG3 criteria. The appearance of new lesions on a bone scan should be confirmed on a subsequent bone scan before determining disease progression based on these results. If a participant

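### SAP 4.2 defines the Safety Population by RP-3467 alone although other SAP rules count either drug, and the pre-dose event summary in 10.2 names no population

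*SAP*

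**What the plan says.** SAP 4.2 states that the Safety Population "will consist of all participants who receive at least 1 dose of RP-3467". It then gives the set its scope: "The analysis set will be used for individual listings, disposition summary table and all safety analyses, unless otherwise specified". SAP 10.2 repeats the default for adverse events: "Overall AE summaries will be presented for the Safety Population (unless otherwise specified)".

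Other sections count either drug. SAP 5.1 takes baseline as the last value "prior to the first administration of RP-3467 or olaparib, whichever occurs first". SAP 5.2 ends the treatment-emergent period by reference to the last dose of RP-3467 or olaparib. SAP 5.6 and 5.7 impute dates against whichever drug came first, and 10.2 defines a TEAE by exposure to the trial intervention(s).

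The DLT analysis has its own set. SAP 10.1 says: "The number of DLTs will be summarized by treatment arms for the DLT Evaluable Population". SAP 4.1 admits to that set, by one of its two routes, participants "who experience a DLT at any time during the DLT evaluation period (from the start of treatment through the end of Cycle 1)".

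For events before dosing, 10.2 says: "Prior to receiving trial intervention, only AEs considered related to trial procedures and all SAEs will be summarized". The grouping is by arm, dose level and schedule, and no population is given. Table 5, footnote r, places a trial procedure in that window for Arm 1: "Tumor biopsies will be collected during Screening and on C1D17".

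**The concern.** Safety and tolerability of RP-3467, alone and with olaparib, is the primary objective, and each combination dose level starts with 3 participants. At that size the reader should be able to account for everyone who took a trial drug.

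Two kinds of participant are at issue. The first is an Arm 2 participant who takes olaparib and stops before any RP-3467. The SAP dates that person's baseline and events from olaparib, but 4.2 then leaves the person out of the set on which those events are tabulated. The second is a participant who consents, has a serious event from a Screening procedure and is never dosed. The event is collected from consent, yet the default population contains only dosed participants. Among pre-dose events, those serious enough to prevent dosing are the ones at risk of not being reported.

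**Working it through.** There is no planned figure to reproduce. The check is to follow each case through the outputs that the SAP names.

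**Case A: Arm 2 participant with olaparib only**

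| Output | Population named | Participant included? |
|---|---|---|
| TEAE and SAE summaries (10.2) | Safety | No |
| Laboratory, vital signs, ECG (10.3 to 10.5) | Safety | No |
| Exposure, including olaparib exposure (6.6) | Safety | No |
| Disposition, including number treated and reason for stopping (6.2) | Safety | No |
| DLT summary (10.1) and DLT row of the AE overview (10.2) | DLT Evaluable | Yes, if a Cycle 1 DLT occurred |
| MDS/AML listing (10.2) | Described by olaparib treatment | Possibly, if the event occurred |

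The DLT row follows from 4.1, which has two routes:

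- *By exposure.* At least 75% of the planned Cycle 1 dose of RP-3467 is required. This participant has 0%, so the route is closed.
- *By event.* A DLT after the start of treatment is enough. No RP-3467 dose is required, and 10.1 asks for a possible relation to trial treatment, not to RP-3467 specifically. The route is open.

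Two results follow. With a DLT, the participant is in the DLT Evaluable set and outside the Safety Population, so the first is not a subset of the second. The AE overview would then count a DLT whose event is missing from the TEAE rows of the same table. Without a DLT, the participant is in neither set, and SAP 2.3 allows another to be added in their place.

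**Case B: Screening event, never dosed**

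1. AEs are recorded from consent (10.2).
2. Arm 1 has a Screening biopsy (Table 5, footnote r), and eligibility must still hold before the first RP-3467 dose (Table 5, footnote a). A route from procedure to event to no dosing therefore exists.
3. The pre-dose summary and the closing sentence of 10.2 on listings name no population. The 4.2 default covers individual listings, so on that default the participant is omitted.
4. The summary is grouped by dose level, and a never-dosed participant may have none.

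**Illustration of size** (assumes exactly one olaparib-only participant)

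- Share of a three-person cohort: 1/3 = 33.3%. If that person is replaced and three others are dosed: 1/(3+1) = 25.0%.
- Share of planned Arm 2 escalation (about 24, SAP 2.3): 1/24 = 4.2%.
- Direction of a rate: suppose 1 of 3 RP-3467-treated participants has a given event, 1/3 = 33.3%. Adding an olaparib-only participant with the event gives 2/4 = 50.0%; adding one without it gives 1/4 = 25.0%. The rate can move either way.

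**The case against.** A reader might go further and infer that the Safety Population governs every safety table and listing, so that these participants appear nowhere. The documents do not support that. SAP 4.2 allows for exceptions, the DLT outputs use another set, and the MDS/AML listing is framed by olaparib treatment. For the never-dosed participant, the reference in 10.2 to all SAEs, and its closing sentence on listing all AEs and SAEs, can be read as such an exception. That half is an ambiguity, not a stated exclusion. Parts of SAP sections 4 and 6.2 are also removed from the public text, so absence from every output could not be shown in any case.

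A reader might also infer that combination toxicity is under-reported in one direction. Omitted events do lower counts, but an event-free olaparib-only participant would only change the denominator. Someone who never took RP-3467 has not received the combination, and requiring a dose of the investigational drug is a defensible choice if it is made openly.

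The strongest objection is rarity. No visible text shows an olaparib-only participant arising by design. Table 5, footnote a, names a first RP-3467 dose on Day -2, and Table 6, footnote a, names one on Day 1. The detailed dosing section of the protocol is not in the public text. This stands, and it limits the weight of the point. It does not remove the mismatch: the SAP's dating rules provide for olaparib being taken first, and the population definition does not.

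**Conclusion.** The point holds in limited form. The RP-3467-only criterion in 4.2 is narrower than the exposure rules in 5.1, 5.2, 5.6, 5.7 and 10.2. Taken as written, it leaves an olaparib-only participant out of all Safety Population outputs while still allowing that person into the DLT set. The pre-dose summary in 10.2 lacks a population, and the default would drop never-dosed participants.

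Restricting TEAE tables to dosed participants is normal and is not criticised here. The faults are that 'dosed' is tied to one of two trial drugs, and that a promised summary has no stated denominator.

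The documents give no expected frequency, and it is probably very low. The figures of 1/3 and 1/24 are shares of participants under an assumed single case, not estimates of bias in any event rate. No effect on dose-escalation decisions is shown, because an olaparib-only DLT would still be counted. This is a cheap improvement of minor severity.

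**What to change.** - **SAP 4.2:** define the Safety Population as all participants who receive at least 1 dose of RP-3467 or olaparib. Flag any olaparib-only participant in the tables and listings. If the sponsor prefers to keep the RP-3467 criterion, 4.2 should give the reason and say where olaparib-only participants are reported.
- **SAP 10.2:** add a listing of procedure-related AEs and all SAEs with onset before the first dose, covering everyone who signed the main consent, dosed or not. A listing avoids the need for a dose level that a never-dosed participant may not have.
- TEAE tables stay on the Safety Population.

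The cost is a few words and one extra listing. The events are already collected from consent, so no new data are needed. The downside is that an olaparib-only participant would enter an Arm 2 denominator without having received the combination, which is why the flag is needed.

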5. DEFINITIONS AND CONVENTIONS FOR DATA HANDLING

All analyses will be performed using SAS® Version 9.4 or higher.

Unless specified otherwise, the analyses of data collected will be descriptive and summaries will be presented separately for each dose level, dose schedule (if applicable) and in total for the specified analysis population. Statistical analysis will be purely descriptive and no formal hypothesis testing or comparative analysis between dose level will be performed. Confidence intervals (CIs) will be constructed at two-side 95% level where appropriate.

Frequency distributions for categorical variables will be provided as the number of subjects in the category and the percentages of the total number of subjects in the given population as noted. Percentages will be reported to one decimal place.

The descriptive statistics for continuous variables will be the number of subjects, mean, standard deviation, median, lower and upper quartile, minimum and maximum. Mean, median will be reported to 1 decimal place, while the standard deviation will be reported to 2 decimal places. Minimum and maximum will be reported the same as the original data.

Summary tables may be replaced with listings when appropriate. For instance, an AE Frequency table may be replaced with a listing if it only contains a few unique PTs reported on relatively few subjects.

All tables will be summarized by treatment regimen (Arm 1 and Arm 2 respectively), dose level, and dose schedule, and include an overall column for Arm 1 and Arm 2 respectively unless otherwise specified.

All listings will be sorted by arm, dose level, and dose schedule if applicable, subject ID and, if applicable, by visit date unless otherwise specified in the text.

5.1 Definition of Baseline

For all evaluations unless otherwise noted, baseline is defined as the most recent non-missing measurement prior to the first administration of RP-3467 or olaparib, whichever occurs first.

- Change from baseline is calculated as (Value at a visit – Baseline Value)
- Percent change from baseline is calculated as (Value at a visit – Baseline value)/Baseline value * 100

5.2 Definition of Treatment Emergent Period

Unless otherwise stated, derivations of the worst post-treatment value will be assessed within the confines of the treatment emergent period, defined as the time from the start of study treatment, until 30 days after the last dose of RP-3467 or olaparib, the participant starts a subsequent anti-cancer therapy, or the participant is taking the monotherapy treatment and starts olaparib treatment, whichever occurs first.

5.3 Definition of Resue Period

For rescue arm patients who have been crossed over to the protocol-defined rescue treatment (combination therapy after treatment with monotherapy), the rescue period is defined as the time between the first dose of the co-therapy olaparib to study treatment discontinuation.

5.4 Definition of Study Days

Unless otherwise noted, study days of an evaluation are defined as the number of days relative to the first dose date which is designated as Day 1, and the preceding day is Day -1, the day before that is Day -2, etc.

Study days are calculated as

- (Date of assessment – first dose date + 1) for assessments on/after first dose date.
- (Date of assessment – first dose date) for assessments before first dose date.

5.5 Analysis Visit Window

Data will be analyzed by scheduled visits, where appropriate. Data collected from an unscheduled visit will not be included in the by-visit summary tables but will be presented in the listings. However, data collected at Unscheduled Visit will also be considered for toxicity grading for laboratory assessments. [REDACTED]

5.6 Handling of Missing/Partial Dates for Adverse Events

If the start or end date for an AE is partially or completely missing, the date will first be queried for resolution if possible. If the year of the start date is missing or the start date is completely missing, the first dose date will be used. If the year of the end date is missing or the end date is completely missing, the event will be regarded as ongoing. Impute AE end date first if both AE start date and end date are partially missing.

If end date of an adverse event is partially missing, impute as follows:

- If the day of the month is missing, the onset day will be set to the last day of the month.
- If the onset day and month are both missing, the day and month will be assumed to be December 31.
- If the imputed end date > death date, then set to death date.

If start date of an adverse event is partially missing, impute as follows:

- If the day of the month is missing, the onset day will be set to the first day of the month unless it is on or after the same month and year as study treatment. In this case, the onset date will be assumed to be the first dose date of treatment or co-therapy, whichever comes first.
- If the onset day and month are both missing, the day and month will be assumed to be January 1 when the year is on or after the year of study treatment. If the year is prior to year of first dose, December 31st will be used. The event onset will be coded to the first dose date of treatment if year is the same as the year of first dose date to conservatively report the event as treatment-emergent.
- If the imputed AE start date is after the AE end date (maybe imputed), then update the AE start date with the AE end date as the final imputed AE start date.
- If the imputed start date > death date, then set to death date
- If the imputed end date is before imputed start date, the AE event will be treated as treatment emergent AE and report it as data issue.

Imputation of partial dates is used only to determine whether an event is treatment-emergent or the duration of the event. A flag will indicate if the start or end date was imputed respectively. Data listings will present the partial date as recorded in the eCRF.

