5.7 Handling of Missing/Partial Dates for Non Anti-cancer Medications/Procedures/Therapy

When the start date or end date of a medication/therapy/procedure, that is not anti-cancer therapy, is partially missing, the date will be imputed to determine whether the medication/therapy/procedure is prior or concomitant. The following rules will be applied to impute partial dates for medications. The first dose date will be the date of the first dose of RP-3467 or olaparib, whichever occurs first.

If the start date of a medication/procedure/therapy is partially missing, impute as follows:

- Medication/procedure/therapy start dates with a missing day and non-missing month will be assumed to have occurred on the first day of the non-missing month if the month and year is after first dose date. If the month and year are prior to the first dose date, the last day of the month will be assigned to the missing day. If the month and year are the same as the first dose date, the first dose date will be used.
- Medication/procedure/therapy start dates with missing day and month will be assumed to have occurred on the first day of the non-missing year (i.e., 01 January) if the year is after the year of first dose date. If the year is prior to the year of first dose date, December 31 will be assigned to the missing fields. If the year is the same as the year of the first dose date, the first dose date will be used.
- If the imputed start date > death date, then set to death date and report it as data issue

If the end date of a medication/procedure/therapy is partially missing, impute as follows:

- Medications/procedure that are not ongoing and have a medication/procedure/therapy stop date with a missing day and non-missing month will be assumed to have stopped on the last day of the non-missing month.
- Medications/procedure that are not ongoing and have a medication/radiotherapy stop date with a missing month will be assumed to have stopped on the last day of the non-missing year (i.e., 31 December).
- If the imputed end date > death date, then set to death date and report it as data issue.
- If the imputed end date is before imputed start date, report it as data issue.

If the year of the start date or the year of the end date of a medication/procedure/therapy is missing, or the start date or end date is completely missing, do not impute.

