- Adverse Event of Special interest (AESI) if any occurred as defined in the protocol
- TEAE leading to Death

Any missing onset date, causality, or severity must be queried for resolution. Unresolved missing causality will be considered “Related”.

Any missing or partial dates will be handled according to the rules outlined in section 5.4.

TEAEs will be summarized by SOC, PT unless stated otherwise. TESAEs, Related TEAEs, TEAEs leading to dose modification, TEAEs leading to drug withdrawn, TEAEs leading to death will be summarized in a similar manner.

Summaries tables will be sorted by decreasing frequency of subjects within each SOC and then similarly by decreasing frequency of subjects within each PT. In the case of equal frequency of number of subjects in SOCs or PTs, summaries will be sorted in descending order. Sorting will be based on the total frequency in the combination therapy arm for safety [REDACTED] summaries, and across both arms for all other tables, unless stated otherwise.

Myelodysplastic syndrome (MDS) or Acute myelogenous leukemia (AML) are considered AESIs. These are applicable only to participants treated with olaparib will be listed with details if they occur.

If a SOC or PT was reported more than once for a subject, the subject would only be counted once in the incidence for that SOC or PT.

All AEs, SAEs, DLTs, and will be listed by patient, along with information regarding onset, duration, relationship and severity to study drug, action taken with study drug, treatment of event, and outcome.

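### The SAP 5.6 rule for AE onsets with a missing day moves events from months after olaparib start back to the first RP-3467 dose, so in Arm 1 crossovers they count as monotherapy TEAEs

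*SAP*

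**What the plan says.** SAP 5.6 has partial AE dates queried first and imputes those that stay unresolved. For an onset with a known month and year but no day, the default is the 1st, with this proviso: "unless it is on or after the same month and year as study treatment. In this case, the onset date will be assumed to be", namely the earlier of the first dose dates of study treatment and co-therapy. The section then gives the purpose: "Imputation of partial dates is used only to determine whether an event is treatment-emergent or the duration of the event".

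Three other sections define the periods to which that date is compared:

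- SAP 5.2 ends the treatment-emergent period at the earliest of several events, the last being "or the participant is taking the monotherapy treatment and starts olaparib treatment, whichever occurs first".
- SAP 10.2 puts the same limit in the TEAE definition: "or the participant is taking the monotherapy treatment and starts the co-therapy olaparib, whichever occurs first".
- SAP 5.3 starts a separate period at that point: "the rescue period is defined as the time between the first dose of the co-therapy olaparib to study treatment discontinuation".

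For non-anticancer medications, SAP 5.7 separates the cases that 5.6 merges. A start in the first-dose month takes the first dose date. A start in a later month takes the "first day of the non-missing month if the month and year is after first dose date".

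**The concern.** Imputing the first dose date is a sensible conservative choice when the known month is the month of first dose, because the event may have started on either side of that dose. When the known month is later, there is no such doubt: the event began after dosing. Moving it back to first dose discards information that was collected.

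For most participants this changes only the duration. Crossovers are different, because they have a second boundary, the start of olaparib, and the imputed date decides on which side of it an event falls. The protocol lets Arm 1 participants add olaparib after progression, so their RP-3467 start always comes before their olaparib start and is always the date chosen. An event from the combination phase is then placed at the start of monotherapy.

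At stake is the RP-3467 monotherapy TEAE profile, a primary endpoint tabulated by arm and dose level in small groups.

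**Working it through.** **Inputs from the documents.** SAP 2.3 plans about 12 participants in Arm 1 over up to 4 dose levels, so 12/4 = 3 per level. SAP Table 2 runs to 9 participants at one level. The rules are those of SAP 5.2, 5.3, 5.6, 5.7 and 10.2. The plan states no figure of its own on this point to reproduce.

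**Illustrative dates (assumed).** First RP-3467 dose 10 Feb 2025; olaparib added 1 Jun 2025; AE with onset in July 2025, day unknown, ending 20 Jul 2025.

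**Step 1: imputed onset.**

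| | SAP 5.6 as written | First of the known month |
|---|---|---|
| Imputed onset | 10 Feb 2025 | 1 Jul 2025 |
| Position relative to olaparib start | 1 Jun − 10 Feb = 111 days before | 1 Jul − 1 Jun = 30 days after |
| Period | monotherapy treatment-emergent | rescue |
| Duration | 20 Jul − 10 Feb + 1 = 161 days | 20 Jul − 1 Jul + 1 = 20 days |

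The excess duration equals the first of the AE month minus the first dose date. It is 19 days for a March onset (1 Mar − 10 Feb) and 141 days for July (1 Jul − 10 Feb).

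**Step 2: does another rule in 5.6 repair this?** No. The start-after-end correction applies only if the imputed start is later than the end. With the start set to first dose, the event would have to end before first dose, which an event from a later month cannot do. The death-date cap can only move a start earlier.

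**Step 3: consistency within 5.6.** When day and month are both missing and the year is after the year of first dose, the onset becomes 1 January of that year. With first dose on 10 Feb 2025, an onset known only as 2026 goes to 1 Jan 2026, while one known as February 2026 goes to 10 Feb 2025. The better-documented date is moved further from the truth.

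**Step 4: effect on incidence.** For one participant who did not already have the preferred term on monotherapy:

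- Arm 1 total: 1/12 = 8.3 percentage points.
- Level with 3 participants: 1/3 = 33.3 points.
- Level with 9 participants: 1/9 = 11.1 points.

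The documents give neither a crossover rate nor a rate of unresolved partial dates. For an assumed 0, 1 or 2 such participants, the Arm 1 total for that term rises by 0, 8.3 or 16.7 points (2/12).

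**Step 5: what the SAP 5.7 rule leaves open.** A missing-day onset in the crossover month itself still needs a rule. If olaparib had started on 14 April, an April onset would be set to 1 April, 13 days before olaparib, and would count as monotherapy. SAP 5.7 has no crossover provision to copy.

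**The case against.** The strongest reply is that the conditions are narrow. The participant must cross over, which the protocol ties to progression, eligibility, no Grade >2 drug-related toxicity and Medical Monitor approval. The onset day must remain unknown after a query, the month must fall after olaparib start, and the preferred term must be new for that participant. RP-3467-related SAEs drop out altogether, because SAP 10.2 counts them as TEAEs whenever they start. The listings show the recorded partial date with an imputation flag, for crossovers as for everyone else, so an affected event can be traced. The wording may also be a slip, since SAP 5.7 and the next bullet of 5.6 treat later periods differently. Finally, the visible text defines a rescue period but no AE table for it, so a corrected event might appear only in listings.

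Most of this stands as a limit on size. The frequency is unknown and may be zero, 33.3 points is the 3-participant case, and a participant who already had any monotherapy TEAE leaves the overall TEAE count unchanged. None of it makes the rule right. Flags and listings do not correct the incidence tables, and a slip in a SAP is programmed as written. After correction, these events would be handled like any fully dated event in the rescue period. Parts of the SAP are removed or redacted, so rescue-period reporting cannot be called absent.

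**Conclusion.** The concern holds. As written, SAP 5.6 assigns a missing-day AE from a month after olaparib start to RP-3467 monotherapy in an Arm 1 crossover, contrary to the windows in SAP 5.2, 5.3 and 10.2, and no visible rule corrects it. The increments in Step 4 rest on the planned Arm 1 size and on assumed counts of affected participants; they are not an estimate of what will occur.

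For participants who do not cross over, TEAE status is normally unchanged and only duration is inflated; in the visible text, duration is a listing item. An event recorded more than 30 days after last dose, or after new anticancer therapy, would also be pulled into the window, but SAP 10.2 stops routine AE collection at those points. No effect on DLT decisions is shown. This should be corrected, mainly because it touches a primary endpoint and costs little to put right.

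**What to change.** 1. In the missing-day bullet of SAP 5.6, apply the first dose date only when the onset month and year equal those of first dose. For later months use the first day of the known month, as SAP 5.7 does.
2. State how a missing-day onset in the month of olaparib start is attributed, and justify the direction. Using the olaparib start date could remove a true monotherapy event; using the first of the month could add a combination event.
3. For clarity, reword the bullet for missing day and month so that 1 January applies to years after the year of first dose and the first dose date applies to the same year.
4. Correct the cross-reference in SAP 10.2, "Any missing or partial dates will be handled according to the rules outlined in section 5.4". Section 5.4 defines study days; the AE date rules are in 5.6.

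The cost is SAP wording and a small programming change. Trial conduct is not affected.
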